3.6.4. Vital signs, clinical examination and other observations related to safety

3.6.4.1. Vital signs and clinical examination

Definition:

- A value is considered as analysable if collected under appropriate circumstances.
- The analyses will be performed separately for periods #2, #4 and #6.
- A value is considered as occurring during the considered period if the associated visit date is between the start and last date of the considered period.
- Baseline for each period is defined in Section 3.1.2.

Analyses

The following vital signs and clinical examination will be analysed:

- Weight (kg).
- BMI (kg/m^2) (quantitative value and by class).
- HR (b.p.m).
- SBP (mmHg).
- DBP (mmHg).

Quantitative parameters will be described separately for each period, in terms of value at baseline, value at each planned post-baseline visit under treatment as well as in terms of change from baseline to each planned post baseline visit under treatment.

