4. STUDY DESIGN

4.1. Endpoint(s)

Table (4.1) 1 - Endpoints

	Objectives	Endpoints
Primary	To demonstrate the superiority of bumetanide (0.5mg BID) oral liquid formulation as compared to placebo in the improvement of ASD core symptoms after 6 months of treatment in children aged from 2 to less than 7 years old with ASD	Childhood Autism Rating Scale, Second Edition (CARS2) total raw score. Main expression will be change from baseline to 6 month.

	Objectives	Endpoints
Secondary	To assess the effect of bumetanide on the other efficacy endpoints	
 - The change in SRS-2 total raw score from baseline to 6 month - CGI-I score at 6 month - The change in VABS II subscores from baseline to 6 month - The change in each individual CARS2 domain from baseline to 6 month
	To assess the safety of bumetanide	
 - Adverse events (AE), Paediatric Adverse Event Rating Scale (PAERS) - Clinical laboratory evaluation - Vital signs and clinical examination: weight (kg), height (m), Body Mass Index (BMI) (kg/m²), systolic blood pressure (mmHg), standing, sitting; Diastolic blood pressure (mmHg), standing, sitting, heart rate (bpm) - Electrocardiogram - Renal ultrasound - Assessment of suicidal ideation and suicidal behaviour using the Columbia Suicide Severity Rating Scale Children's version (C-SSRS-C)
	To confirm the acceptability and palatability of the oral liquid formulation	Acceptability and palatability questionnaire
	To describe the bumetanide effects on patients' quality of life	
 - Paediatric Quality of Life Inventory (PedsQL) expressed in term of change from baseline to month 6 - WHOQOL-Bref questionnaire summarized at each planned visit for each period using descriptive statistics
	To improve existing pharmacokinetic model of bumetanide in this population	PK points at W012 and W026
Exploratory	To describe the Bumetanide effect on utility index scores	Utility index score on the EQ-5D-3L

Refer to sections 6.1 and/or 7.1 for further details.

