8.2. Methods and measurement times

The **Columbia Suicide Severity rating Scale Children's version (C-SSRS-C)** ([Posner, 2007](#)) ([Posner, 2011](#)) assesses suicidal ideation and suicidal behaviour. Investigator will complete an e-training on this tool prior to the study start.

The C-SSRS-C includes two forms:

- Baseline/Screening version: completed at W000

- Since Last Visit version: to be completed at W012, W026, W038, W052 or at the withdrawal visit in case of premature withdrawal

The **Paediatric Adverse Event Rating Scale (PAERS)** (Shapiro, 2009) is an inventory report designed to identify signs/symptoms experienced by the patient since the study treatment initiation. Investigator will complete an e-training on this tool prior to the study start.

The PAERS will be completed:

- o During the Double Blind period at: W000, W000+Day 17, W004, W008, W012, W016, W020, W026 visits
- o During the Open Label period at: W026+Day17, W030, W034, W038, W042, W046, W052 visits
- o At the withdrawal visit in case of premature withdrawal

PAERS includes three forms:

- Youth form, to be completed when possible by the patient,
- Parent form, to be completed by a parent/legal representative or caregiver (when applicable).
 - o As far as possible same person should complete the form during the study
- Clinician form filled after assessment of youth form and parent forms

Physical examinations

- DBP, SBP and heart rate must be always assessed. Appropriate conditions are assessment in a sitting or lying position after 5-minute rest and at 1mn after standing position (orthostatic hypotension: known effect of bumetanide):
 - o At Selection
 - o During the Double Blind period at: W000, W002, W012, W026 visits
 - o During the Open Label period at: W028, W038, W052 visits
 - o At the withdrawal visit in case of premature discontinuation.DBP and SBP will be measured with the specific device provided by the Sponsor for the study.
- Body weight must be assessed:
 - o At Selection
 - o During the Double Blind period at: W000, W000+Day17, W004, W008, W012, W016, W020, W026 visits
 - o During the Open Label period at: W026+Day17, W030, W034, W038, W042, W046, W052 visits
 - o At the withdrawal visit in case of premature withdrawal.
- Height must be assessed:
 - o At Selection
 - o During the Double Blind period at: W012, W026 visits
 - o During the Open Label period at: W038, W052 visits
 - o At the withdrawal visit in case of premature withdrawal

12-lead ECG

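### The SAP's vital-signs list omits height, leaves the sitting and standing readings undefined, and gives no growth-standardised weight or BMI for the single-arm periods

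*SAP*

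**What the plan says.** Protocol Section 4.1 (endpoint table) lists among the safety endpoints "weight (kg), height (m), Body Mass Index (BMI"), and then "systolic blood pressure (mmHg), standing, sitting", with diastolic pressure in the same two positions and heart rate.

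Protocol Section 8.2 requires blood pressure and heart rate after 5 minutes' rest and again 1 minute after standing. The reason given is "orthostatic hypotension: known effect of bumetanide". The same section states "Height must be assessed" and names selection, W012, W026, W038, W052 and the withdrawal visit.

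SAP Section 3.6.4.1 introduces its list with "The following vital signs and clinical examination will be analysed". The list is weight (kg), BMI (kg/m²), heart rate, SBP and DBP. BMI is to be shown as "quantitative value and by class", and the classes are not defined. The analysis is descriptive: baseline, value at each planned visit under treatment, and change from baseline.

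SAP Section 3.6 describes the double-blind period by arm against placebo. It describes the open-label period in the Placebo/S95008 arm only and the combined period in the S95008/S95008 arm only.

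**The concern.** There are three gaps between what is measured and what is summarised.

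- **Height.** It is an endpoint with a visit schedule and no planned analysis.
- **Orthostatic readings.** The standing measurement exists to detect a named drug effect. That effect is a within-child contrast between two positions, and the SAP neither computes the contrast nor says which position its SBP and DBP refer to.
- **Growth.** Participants are 2 to under 7 years old and are followed on treatment for up to 12 months. Where there is no comparator, a rise in raw weight is expected whether or not gain has slowed.

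At stake is the usefulness of the long-term safety description, which the protocol (Section 2) gives as the purpose of the open-label period.

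**Working it through.** The documents give no figure for this point, so the main check compares the two lists.

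| Item | Protocol 4.1 and 8.2 | SAP 3.6.4.1 |
|---|---|---|
| Height | Endpoint; selection, W012, W026, W038, W052 | Not listed |
| Weight, BMI | Endpoints | Listed in raw units; BMI classes undefined |
| SBP, DBP | Endpoints, standing and sitting | Listed; position not stated |
| Heart rate | Measured at rest and after standing | Listed; position not stated |
| Standing minus resting | Reason for the standing reading is given | Not planned |

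Neighbouring SAP sections go further for other risks. Laboratory values get cut-offs for potentially significant values and shift tables, potassium gets severity classes (both 3.6.3), and QTc gets classes (3.6.4.2).

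The illustrations below show why the gaps matter. Apart from the roughly 100 children per arm planned in the protocol, **their inputs are assumptions that are not in the documents**. The SAP plans no tests here, so power serves only as a gauge of visibility.

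**1. Orthostatic falls.** Suppose a fraction f of bumetanide children has a 20 mmHg standing SBP fall, with an SD of SBP change of 8 to 12 mmHg and 100 children per arm.

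- Shift in mean standing SBP = 20 × f.
- Power = Φ(shift / (SD × √(2/100)) − 1.96). For f = 0.10 and SD = 10: 2 / 1.414 − 1.96 = −0.546, so power is 0.29.
- The count comparison is a two-proportion test against an assumed placebo rate of 1–2%. This is a rough approximation at such small counts.

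| f | Mean shift (mmHg) | Power, standing mean | Power, positions averaged (same SD) | Expected count, bumetanide vs placebo | Power, count |
|---|---|---|---|---|---|
| 5% | 1 | 0.09–0.14 | 0.05–0.07 | 5 vs 1–2 | 0.21–0.38 |
| 10% | 2 | 0.22–0.42 | 0.09–0.14 | 10 vs 1–2 | 0.67–0.80 |
| 20% | 4 | 0.65–0.94 | 0.22–0.42 | 20 vs 1–2 | about 0.99 |

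If only sitting values were summarised, this signal would be absent.

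**2. Raw weight without a comparator.** If normal gain is g and it slows by a fraction r, observed gain is (1 − r) × g, which is positive for any r below 1. With g assumed at 1.5 to 3 kg a year and r = 0.5, the observed 12-month gain is +0.75 to +1.5 kg. The raw mean still rises, whereas a score standardised for age and sex would fall.

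**3. BMI as a stand-in for height.** At equal weight, 1 cm less height changes BMI by (h/(h − 1))² − 1. For assumed heights of 95, 105 and 115 cm this is +2.1%, +1.9% and +1.8%. Raw BMI therefore moves in the opposite direction to a height deficit.

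**4. What the double-blind comparison can show.** The smallest between-arm difference detectable with 80% power is 2.80 × √(2/n) SD: 0.43 SD with 85 per arm and 0.40 SD with 100.

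**The case against.** A reader might infer three stronger conclusions. The documents support none of them.

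- **That growth effects would not be seen.** This fails for the main analysis. Normal growth is expected in both randomised arms, so slower weight gain on bumetanide can appear as a between-arm difference in raw change. The first six months of the combined-period arm fall within that comparison. What stands is the absence of any direct view of height, and the uncontrolled periods.
- **That the standing readings are discarded.** SBP, DBP and heart rate are all on the SAP list, and only the position is unstated. The SAP accepts values taken under appropriate circumstances, and protocol Section 8.2 describes appropriate conditions as covering both positions. Table templates are in a separate document and may split by position. It is fair to say only that the SAP does not state how position is handled.
- **That orthostatic hypotension would go unreported.** Abnormal findings judged clinically relevant are adverse events (protocol 8.3), and treatment-emergent events are tabulated by system organ class and preferred term (SAP 3.6.1). The gap is limited to measured falls that nobody reports as an event. The PAERS scale does not fill it, because the SAP contains no PAERS analysis.

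It is also fair to say that neither document promises standardised growth scores, and that the protocol describes the paediatric safety profile as mainly diuretic without naming slowed growth. The standardisation request is thus an improvement rather than a broken commitment. The omission of height is different, because the protocol lists it as an endpoint.

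**Conclusion.** The point holds as a low-cost improvement. Followed as written, SAP Section 3.6.4.1 leaves one protocol safety endpoint (height) without an analysis. It leaves the orthostatic contrast uncomputed, and it leaves weight and BMI change in the open-label and combined periods inseparable from normal growth. These conclusions rest on the text alone. The numerical illustrations rest on assumed rates, SDs, heights and growth, and show direction and rough scale only. The double-blind comparison of weight and BMI with placebo remains valid, and no efficacy analysis is affected.

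**What to change.** Amend SAP Section 3.6.4.1 as follows:

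1. Add height to the list.
2. Beside the raw values, describe age- and sex-standardised weight, height and BMI (value and change from baseline) from one named growth reference, at least for the open-label and combined periods. Define the BMI classes.
3. Describe SBP, DBP and heart rate by position. Add the standing-minus-resting change and the number of children meeting a pre-specified orthostatic definition, by arm and visit.
4. State which height enters baseline BMI, because only weight is measured at W000.

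Two protocol passages should be reconciled so that the new variables are well defined. Section 8.2 allows a sitting or lying resting reading, while Section 4.1 says sitting. Section 8.2 also names blood-pressure visits at W002 and W028, while the schedule in Section 4.2.2 has Day 17 visits instead.

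The cost is a few derived variables and tables from data already collected, with no added visit. The one real downside is having to choose a single growth reference for all countries (12 planned). Settling it and the orthostatic definition before unblinding avoids a choice made with knowledge of the results.

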3.6.4.2. Electrocardiogram

Definition:

- ECG parameters will be the following: heart rate (b.p.m), RR interval (msec), PR interval (msec), QRS complex (msec), QT and QTcF interval (msec) (Fridericia's correction formula interval).
- A value is considered as analysable if non-missing value obtained from an interpretable ECG.
- An ECG is considered as interpretable if the quality of the trace is "Correct", with "Minor problems" or "Missing data".
- The analyses will be performed separately for periods #2, #4 and #6.
- A value is considered as occurring during the considered period if the assessment date is between the start and last date of the considered period.
- Baseline for each period is defined in Section 3.1.2.

Analyses:

Presence of clinically significant ECG abnormalities will be described as well as sinus rhythm at each planned visit under treatment.

ECG parameters will be described separately for each period, in terms of value at baseline, value at each planned post-baseline visit under treatment; as well as, for quantitative endpoints, in terms of change from baseline to each planned post baseline visit under treatment.

Moreover values and changes from baseline of the concerned period of corrected QT interval will be described in classes (*i.e.*, ≤ 450 ,]450 ; 480[, [480 ; 500] and > 500 msec for values, and ≤ 30 ,]30 ; 60] and > 60 msec for changes).

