26. Patient requiring concomitant psychotropic medication (exceptions reported, See Section 6.3).
27. (A) Patients requiring contraindicated medications (non-exhaustive list):
 - Chronic administration of non-steroidal anti-inflammatory drugs: *risk of NSAIDs nephrotoxicity increased*
 - non-repolarising neuromuscular blocking agents: *hypokaliemia increases the sensitivity to non-repolarising neuromuscular blocking agents*
 - Digitalis glycosides: *Risk of digitalis toxicity secondary to hypokaliemia (and possibly hypomagnesemia)*
 - Antiarrhythmics: *Risk of cardiotoxicity (QT prolongation, torsades de pointe, cardiac arrest) secondary to hypokaliemia (and possibly hypomagnesemia)*
 - Antihypertensive agents (Angiotensin II receptors antagonists, Angiotensin Converting Enzyme Inhibitors) and medicinal products inducing postural hypotension (e.g. tricyclic antidepressants): *Increased risk of postural hypotension*
 - Potassium depleting agents such as other diuretics, laxatives (refer to section 6.3 Previous and concomitant treatments), chronic high doses of mineralo and glucocorticoids, amphotericin B: *The potassium depleting effect of bumetanide may be increased by other potassium depleting agents (other diuretics, laxatives...)*
 - Aminoglycosides: *Ototoxic and nephrotoxic effects of aminoglycosides may be increased by concomitant administration of bumetanide*
 - Probenecid: *Decreased bumetanide effectiveness. Probenecid has been demonstrated to produce a dose related inhibition of bumetanide induced natriuresis*
 - Iodinated contrast products: *Risk of renal insufficiency due to dehydration provoked by a concomitant administration of bumetanide*
 - Lithium: *Bumetanide reduces lithium clearance resulting in high serum levels of lithium*
 - High doses of Vitamin D (> 100 000 IU/3 months) received as a supplement: *Risk of nephrocalcinosis*
 - Desmopressin: *Increased risk of severe hyponatremia*

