relevant hypercalciuria according to their clinical judgment (based on broader sources including risk factors, medical history, clinical examination and other biological parameters).

Additional urinary retest(s) and other appropriate exams should be performed if they judge them as relevant for the patient's safety.

- Absence of 2 consecutive planned electrolytes monitoring analysis.
- Absence of 2 consecutive planned urinary monitoring analysis.
- Occurrence of QT prolongation ($QTc_F \geq 480\text{ms}$), torsade de pointe and ventricular arrhythmia. Even if a 12-lead ECG reading and interpretation will be centralised, a local assessment of ECG exams is necessary for detection of medical urgencies and must be enclosed in the source data. Central reading reports for ECG overrule local reading for inclusion/exclusion/withdrawal criteria.
- Occurrence of a new psychiatric or other medical conditions leading to necessary administration of forbidden concomitant medication or likely to interfere with the conduct of the study.
- Any event or circumstances related or unrelated to the treatment justifying the discontinuation of treatment in the investigator's opinion (including treatment failure i.e. lack of efficacy).
- Major deviation to protocol if it interferes with the study evaluations and/or if it jeopardises participant's safety, e.g. any medical event requiring administration of an unauthorised concomitant treatment (see section 6.3).

Other criteria for premature discontinuation of IMP and for premature withdrawal from the study:

- Lost-to-follow up.
- Any non-medical circumstances leading to patient withdrawal (e.g. assent/consent withdrawal).

Information to be collected during the last visit of these participants is given in Section 5.6.2. These follow-up modalities are used to ensure the efficacy and safety evaluation of all participants who received the IMP.

Special conduct in case of gastrointestinal symptoms and weight loss

If the patient experiences digestive symptoms (≥ 3 liquid stools per day and/or ≥ 3 vomits per day) or digestive symptoms with a weight loss greater than 5%, the study treatment should be temporarily interrupted. Such an interruption will last 48h/72hours.

In such a case a monitoring of K^+ , Na^+ must be done locally prior to study treatment re-introduction. Further electrolytes follow up will be locally done according to the clinical opinion of the medical doctor.

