Investigators should always encourage patients to eat foods containing potassium as soon as they know that they will be included in the study. See [Table \(8.2\) 1](#)

Table (8.2) 1 - Foods that have a higher potassium contents

Fruit and nuts	Fruit in particular - bananas, apricots, avocados, blackcurrants, rhubarb, fresh fruit juices Dried fruits eg currants, raisins, prunes, figs, sultanas, are rich sources of potassium All varieties of nut eg almonds, peanuts and walnuts
Potatoes	Potatoes are very rich sources of potassium if they are not boiled Jacket potatoes Ordinary fried chips Instant potato products eg waffles, potato croquettes Potato crisps
Vegetables and pulses	In particular - sprouts, mushrooms, parsnips, spinach, baked beans, kidney beans, lentils
Cereals	Cereals which are high in bran eg bran flakes, all bran, muesli
Biscuits, cakes and sweets	Fruit cakes, fig rolls, muesli bars Chocolate, fudge, liquorice
Milk and dairy products	Drinking milk or eating yoghurts

The first electrolytes monitoring under treatment, in both double and open label periods, should be performed locally no later than 72h after W000 and W026 respectively.

In case of any abnormality, electrolytes will be monitored until return to normal values.

In case of **Mild Hypokalaemia ($3\text{mEq/L} \leq \text{K}^+ < 3.5 \text{mEq/L}$)** arising under study treatment:

→ Foods containing Potassium will be recommended such as leafy green vegetables, tomatoes, citrus fruits, oranges or bananas. An adequate care should be implemented for the hypokalaemia follow up.

→ Patient will be supplied with oral potassium according to investigator's opinion which can be based on local guidelines or local medical practice. The dose could be adapted to hypokalaemia severity or patients' weight.

The following Potassium Chloride doses are recorded only for indicative purposes:

- <20 kg = 400 mg/day (200 bid)
- 20-40 kg = 600 mg/day (300 bid)
- 40 kg = 1200 mg/day (600 bid)

In case of **Moderate Hypokalaemia ($2.2\text{mEq/L} \leq \text{K}^+ < 3 \text{mEq/L}$)** arising under study treatment:

→ The study treatment should be immediately discontinued.

→ An adequate care should be implemented for the hypokalemia follow up.

→ Cardiac monitoring will be performed and level of potassium should be monitored until return within normal range

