3.6.3. Clinical laboratory evaluation

Definition:

- A laboratory value is considered as analysable if non-missing and not flagged in the ClinTrial database as "not analysable".
- The analyses will be performed on periods #2, #4 and #6.
- A value is considered as occurring during the considered period if the sampling date is between the start and last date of the considered period.
- Baseline for each period is defined in Section 3.1.2.
- For each considered period:
 - High emergent abnormal value under treatment according to the laboratory reference ranges is defined as value \leq ULN (Upper Limit of Normal laboratory reference range) or missing at the baseline of the considered period and $>$ ULN under treatment.
 - Low emergent abnormal value under treatment according to the laboratory reference ranges is defined as value \geq LLN (Lower Limit of Normal laboratory reference range) or missing at baseline of the considered period and $<$ LLN under treatment.

- High emergent abnormal value under treatment according to the cut-offs for PCSA values is defined as value \leq ULS (Upper Limit used to define potentially clinically Significant abnormal values) or missing at baseline of the considered period and $>$ ULS under treatment.
- Low emergent abnormal value under treatment according to the cut-offs for PCSA values is defined as value \geq LLS (Lower Limit used to define potentially clinically Significant abnormal values) or missing at baseline of the considered period and $<$ LLS under treatment.

Analyses:

For each biochemical, haematological (blood and urine sample) parameter and for electrolytes monitoring (Potassium, Sodium), the following analysis will be performed for each period:

- Number and percentage of patients with at least one high/low emergent abnormal value under treatment, according to the laboratory reference ranges and to the cut-offs for PCSA values.
- Laboratory parameters classified (number and percentage of patients in each class) according to these reference ranges and cut-offs and using shift tables from baseline in the considered period to the worst (high and/or low) values under treatment.

Moreover, listings of patients with out-of-range or PCSA analysable values emergent under treatment in each period and of non-analysable values excluded from analyses will be provided.

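### SAP 3.6.4.2 defines no worst on-treatment QTcF per child and no time point for the QTcF classes, so a by-arm count of children ever at QTcF ≥ 480 ms is not assured

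*SAP*

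**What the plan says.** **ECG analysis (SAP 3.6.4.2).** Three sentences matter.

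- The parameters are described at baseline, then by "value at each planned post-baseline visit under treatment; as well as, for quantitative endpoints, in terms of change from baseline" to each planned visit.
- Abnormalities: "Presence of clinically significant ECG abnormalities will be described as well as sinus rhythm at each planned visit under treatment". It is unclear whether the visit phrase governs the abnormalities or only sinus rhythm.
- Classes: "Moreover values and changes from baseline of the concerned period of corrected QT interval will be described in classes". The value classes are ≤ 450, above 450 to below 480, 480 to 500 inclusive, and > 500 ms. The change classes are ≤ 30, above 30 up to 60, and > 60 ms. No time point is given.

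The same section places an ECG in a period by its assessment date.

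**Laboratory analysis (SAP 3.6.3).** It counts patients with at least one emergent abnormal value and classifies results "using shift tables from baseline in the considered period to the worst (high and/or low) values under treatment". It also counts patients with hypokalaemia by severity.

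**Why QT is a named risk (protocol).** Section 5.2.2 gives as the reason for barring antiarrhythmics: "Risk of cardiotoxicity (QT prolongation, torsades de pointe, cardiac arrest) secondary to hypokaliemia". Section 5.6.1 makes QTcF ≥ 480 ms a criterion for stopping study drug, together with "torsade de pointe and ventricular arrhythmia".

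**ECGs performed (protocol 8.2).** Four are planned in the double-blind period (W004, W008, W012, W026), and one at the withdrawal visit. Clinically significant findings are followed until normal or stable.

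**The concern.** The plan will count how many children in each arm ever had low potassium. For QT prolongation, which the protocol treats as a possible consequence of low potassium, it specifies no matching count. The class limits include a cut at exactly the protocol's stopping value, yet no table is defined that says how many children ever crossed it.

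By-visit summaries have two weaknesses here. They have no stated place for an ECG taken between visits, such as a repeat after a suspicious tracing. And a child taken off drug after such an ECG is missing from the on-treatment figures at later visits. Because the class sentence is silent, the choice between by-visit and worst-value tables could also be made after unblinding.

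At stake is a by-arm safety figure on an identified risk in young children. The primary efficacy analysis, sample size and type I error are not affected.

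**Working it through.** The plan states no figure to reproduce. The check compares the sections and then asks what by-visit tables can and cannot give.

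**1. Laboratory against ECG**

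| Summary | Laboratory (SAP 3.6.3) | ECG (SAP 3.6.4.2) |
|---|---|---|
| Worst on-treatment value per child | Specified | Not specified |
| Children with at least one abnormal value | Specified | Not specified |
| Value at each planned visit | Not specified | Specified |
| Time point for class tables | Worst value | Not stated |
| Rule placing a value in a period | Sampling date | Assessment date |

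The ECG date rule does not itself exclude unscheduled ECGs. The gap is that no summary is clearly assigned to use them.

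**2. Can the existing classes give the count?** Yes. The classes 480–500 (lower limit inclusive) and > 500 together are exactly QTcF ≥ 480 ms. Only the per-child rule is missing.

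**3. What by-visit tables give at 480 ms.** Reaching this limit stops study drug, so a child should not reappear above it at a later on-treatment visit. Planned-visit counts would then add up to nearly the ever-count. What could be lost is the child whose only ECG at or above 480 ms is off schedule or late. The documents give no rate for this.

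**4. What by-visit tables give for a rise > 60 ms.** No stopping rule attaches to this class, so the same child can recur. Let p be the share above the limit at each of the four double-blind ECGs, with all children attending (both assumptions). The share ever above it is bounded by

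p ≤ P(ever) ≤ 4p,

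and equals 1 − (1 − p)⁴ if visits are independent. The correlated figures take four equally correlated normal values with the threshold set to give p.

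| Assumed p | Bounds | Independent | Correlation 0.5 | Correlation 0.7 |
|---|---|---|---|---|
| 2% | 2% to 8% | 1 − 0.98⁴ = 7.8% | 6.4% | 5.3% |
| 5% | 5% to 20% | 1 − 0.95⁴ = 18.5% | 14.4% | 12.0% |

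At about 100 children per arm, 2% is two children in each visit table and anywhere from two to eight distinct children. The visit tables cannot tell these apart. The rates are illustrative; neither document gives one.

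**5. Withdrawal ECGs**

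- Protocol 5.6.2 allows the withdrawal visit up to one week (7 days) after the last dose.
- SAP Table (3.6) 1 closes the on-treatment periods used for ECG at last intake + 2 days (for the double-blind period, or at the first open-label intake if earlier).
- 7 − 2 = 5: a withdrawal ECG taken on days 3 to 7 after the last dose falls outside the on-treatment ECG analysis, whichever way the class sentence is read.

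**The case against.** **The SAP does not say that unscheduled ECGs are dropped.** This stands. A reader might infer that QTcF classes are tabulated only at planned visits, so that a child stopped on an off-schedule ECG counts as zero. The class sentence carries no visit restriction, and the date rule would admit such ECGs. By visit is the natural reading because the sentence follows the planned-visit one, but it is an inference. The table templates are in a separate document and may settle it.

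**QT stops are reported elsewhere.** Partly stands. Treatment-emergent adverse events leading to withdrawal are tabulated by organ class and preferred term, by arm in the double-blind period (SAP 3.6 and 3.6.1). So the documents do not support saying that children stopped for QT prolongation vanish from by-arm reporting. But under protocol 8.3 an abnormal finding is an adverse event only if the investigator deems it clinically relevant. The listing in protocol 10.2.2.6.3.2 is a yes/no per child. Neither counts measured values.

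**The multi-visit arithmetic does not fit the stopping limit.** This stands. It is used above only for the class with no stopping rule. Children with QTcF ≥ 460 ms are also excluded at entry (protocol 5.4), so rates at 480 ms may be low.

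**Monitoring after low potassium may yield no study ECG.** This stands. For potassium from 2.2 to below 3 mEq/L, protocol 8.2 stops treatment and says "Cardiac monitoring will be performed and level of potassium should be monitored until return within normal range". It does not say that this produces a 12-lead ECG for central reading, so the point does not rely on it.

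**Conclusion.** The point holds as a gap in specification. SAP 3.6.4.2 defines no maximum on-treatment QTcF, no maximum change and no ever-abnormal count per child, and leaves the time point of the QTcF classes open. A by-arm number of children ever at QTcF ≥ 480 ms, or ever with a change > 60 ms, is therefore not assured.

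The size is uncertain. At 480 ms the shortfall is confined to cases seen only on unscheduled or late ECGs, provided the stopping rule is followed. For the > 60 ms class the ever-count could be up to four times the per-visit figure under the assumptions shown. This should be corrected before unblinding, but it is a reporting matter in a descriptive safety section. It does not show that harm will be hidden, and it raises no question about the stopping rule.

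**What to change.** Keep the by-visit tables and add to SAP 3.6.4.2:

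- For each period, and by arm where there are two, the number and percentage of patients by maximum QTcF and by maximum change from baseline, in the existing classes. Use all interpretable, centrally read ECGs dated within the period: planned, unscheduled and withdrawal visit.
- A row for QTcF ≥ 480 ms, combining the top two value classes.
- The number of patients with at least one clinically significant ECG abnormality.
- A separate summary of withdrawal ECGs taken after the on-treatment window (last intake + 2 days), which the first item cannot capture.
- The number of ECGs per child, by arm.

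**Cost.** A few lines of SAP text, one main table per period and a short withdrawal-ECG summary. The planned and withdrawal ECGs are already to be collected, and protocol 4.3 provides for central assessment of each ECG. No extra procedures, and no change to sample size, alpha or clinical rules.

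**Downside.** A maximum picks up more noise than a single-visit value and grows with the number of ECGs. If unscheduled ECGs are more frequent on bumetanide, the comparison would tilt against it, which is why the ECG counts must be shown alongside.
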